RQ 2: Assess the effects of CGM implementation on nursing workload and factors influencing nursing care delivery. We examine nursing workload and care delivery factors through surveys administered to MICU nurses and through a MICU staff nurse focus group (N=10). *Nursing care delivery factors:* Acceptability of CGM measured by the Acceptability of Intervention Measure (AIM), appropriateness of CGM measured by the intervention appropriateness measure (IAM), and feasibility, measured by the Feasibility of Intervention Measure (FIM). Nursing care delivery factors, evaluation of CGM support, and CGM knowledge will be evaluated through focus groups and CGM Satisfaction Questionnaire (modified for healthcare workers). **Hypothesis:** The use of CGM will significantly reduce nursing workload while increasing frequency of glucose monitoring.

RQ 3: To assess glycemic control among patients receiving CGM in the CGM enabled MICU compared to historical control patients who received POC glucose monitoring in the MICU. Among critically ill patients on CGM (N=100) we will examine time in range (70-180mg/dl), time 100-180mg/dl, time 140-180mg/dl, time in hypoglycemia ($<55\text{mg/dl}$, $<70\text{mg/dl}$), and time in hyperglycemia (180-250mg/dl, $>250\text{mg/dl}$) compared to matched historical control patients using 3-tiered linear mixed models to control for patient, unit, and nurse specific variability. **Hypothesis:** Patients with CGM will exhibit greater time in range (100-180mg/dl, 140-180mg/dl, 70-180mg/dl) and experience less frequent time in hypoglycemia than patients on fingerstick POC.

RQ 4: (exploratory) To assess hospitalization outcomes and conduct economic evaluation of the costs to deliver CGM implementation in the MICU. We will track time and resources needed for CGM implementation including personnel, training, facilities, materials, equipment, and other necessary inputs. *Hospitalization outcomes criteria:* Length of stay [ICU, total stay], cost of stay, cost of CGM vs. standard POC glucose monitoring, discharge level of care [home, SNF], 30-day readmission, morbidity, and mortality. **Hypothesis:** Patients with CGM will experience shorter length of stay, lower cost of stay, will be more likely to discharge to home vs. SNF,

have lower 30-day readmission rate, and experience lower mortality/morbidity than matched historical control patients receiving fingerstick POC in the MICU.

II. Background and Rationale

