Rational/Approach. We will conduct a mixed method analysis to evaluate nursing workload and care delivery factors. Nursing care delivery factors including evaluation of CGM support, acceptance of CGM, perceived feasibility, and CGM knowledge, will be evaluated using a combination of questionnaires and focus groups.

Procedures/Variables and Measures. We will evaluate *nursing care delivery factors* related to CGM implementation support, acceptance of CGM, feasibility, appropriateness, CGM knowledge and satisfaction with CGM as measured by Acceptability of Intervention Measure (AIM), Intervention Appropriateness Measure (IAM), and Feasibility of Intervention Measure (FIM), CGM Satisfaction Questionnaire (modified for healthcare workers) and focus group conducted among nurses in the CGM-enabled MICU. The AIM, IAM, and FIM are brief 5 item Likert-scale questionnaires with each showing a high degree of content validity with alphas for the 3 questionnaires between 0.87 and 0.89.³⁰ CGM Satisfaction Questionnaire (CGM-SAT) is a 44-item measuring satisfaction with CGM over the previous 6 months. The survey has a high degree of validity ($\alpha \geq 0.94$) in adults with type 1 diabetes using CGM.³¹ Several items will be modified for application in healthcare workers. All MICU staff nurses (N=152) will be informed of the study and invited to participate via email. Upon e-consent, the questionnaires will be administered via a REDCap survey. A focus group will be conducted among MICU staff nurses (N=10) to gage their experience using CGM. A semi-structured interview guide will focus on areas of perceived CGM implementation support and education, CGM knowledge, and recommendations for future best practice. All Aim 2 variables and measures appear in Table 2.

RQ 3: To assess glycemic control among patients receiving CGM in the CGM enabled MICU compared to historical control patients who received POC glucose monitoring in the MICU.

Rational/Approach. We will analyze glycemic control factors among MICU patients on CGM compared to 100 historical control patients from the same MICU who receiving only POC glucose monitoring. We hypothesis that patients with CGM will exhibit greater time in range (100-180 mg/dl, 70-180mg/dl, 140-180mg/dl) and experience less frequent time in hypoglycemia than patients on fingerstick POC.

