Aim	Concept	Variables	Frequency	Measure
Aim 2	Nursing care delivery factors	Evaluation of CGM support	Once	
 • Acceptability of Intervention Measure (AIM), Intervention Appropriateness Measure (IAM), and Feasibility of Intervention Measure (FIM) • CGM Satisfaction Questionnaire • Focus groups

Data Management. All data will be labeled with unique identifiers for subject and study, date and time-stamped, and secured in locked filing cabinets in the project office, if hardcopy, on a server housed in a 24/7 offsite university-run networking facility, via web-based data capture, REDCap. To facilitate the HIPAA compliant remote monitoring of CGM data, dummy clinical Clarity accounts will be created for each device/patient. Android phone set-up requires entry of individual Dexcom Clarity account information on each phone.

D. Data Analysis

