Descriptive statistics of central tendency (range, mean, median, and standard deviation) will describe variable characteristics and examine data distribution for normality and outliers. Descriptive statistics will summarize the sample characteristics and distribution of each variable. Data will be screened for normality, outliers, and homogeneity. Continuous variables with normal distribution will be reported as mean (standard deviation) while non-normal distribution will be reported as median (interquartile range). For **RQ1**, multivariate linear models will be used to evaluate clinical utility and implementation variables while examining the effects of patient condition (i.e., sequential organ failure assessment (SOFA) score, renal replacement, ventilator support, pH) as covariates. For **RQ 2**, For qualitative analysis of focus group data, a code book will be developed a priori based on the semi-structured interview questions. Interview data, fieldnotes and memos were imported into NVivo 12.0 (Doncaster, Australia) for data management and analyzed using a qualitative descriptive approach.^{35,36} Two researchers ([name] and [name]) will perform qualitative analysis. Portions of text will be coded with terms that were low inference (“data close”); then grouped into thematic categories and subthemes.³⁵ For **RQ3**, hyperglycemic and hypoglycemic events will be identified for CGM and non-CGM users. Discrete CGM glucose values will be used to aggregate derived measures of glucose variability, including time in target (blood glucose value of 70-180mg/dl), time 100-180mg/dl (representing a more conservative target used inpatient), time 140-180mg/dl (representing institutions IV insulin guideline glycemic target), time above target (>180mg/dl & >250mg/dl), time in hypoglycemia (<70mg/dl & <55mg/dl), glucose standard deviation, and coefficient of variation. Daily percent time in target as well as cumulative time in target will be assessed. Time in target will be derived from ADA glucose targets defining hypoglycemia as a blood glucose less than 70mg/dl and peak post-prandial glucose as <180mg/dl³⁷. The blood glucose range of 70-180mg/dl is consistent with other studies examining time in target.³⁸⁻⁴¹ Measures of hypoglycemia will be in accordance with ADA recommendations for measurement at <70mg/dl and <55mg/dl which is a marker of severe hypoglycemia.⁴² Days with $\geq 70\%$ CGM percent wear, as recommended by ADA, will be included in daily time in target analysis.⁴² For matched historical control patients, percent POC in target (70-180mg/dl), 100-180mg/dl, 140-180mg/dl, percent POC >180mg/dl and percent POC >250mg/dl, percent POC <70mg/dl and percent POC <55mg/dl will be evaluated consistent with other recent studies.^{43,44} For CGM daily glycemic control (i.e., time in range [70-180mg/dl], time 100-180mg/dl, time 140-180mg/dl), linear mixed effect modeling (LMM) for repeated measures will be used to adjust for between subject and within subject variance. A 3-tiered LMM will be used to control for patient, unit, and nurse specific variability. LMM will be repeated for analysis of daily POC glucose control for matched historical control patients for days with ≥ 3 POC fingersticks performed. Two-sided significance level of 0.05 was used for all the statistical tests. For **RQ4**, the cost analysis for the proposed study will be conducted from the provider perspective. Cost estimation involves three major steps: (1) identify the relevant cost items; (2) measure the use of resources; and (3) place a value on the resources used. We will obtain estimated costs for proposed CGM implementation. Direct benefits and savings tend to fall into one of two categories: either savings from enhanced efficiency and productivity, or savings from outcomes improvement (e.g., reducing length of stay, lower 30 day readmissions). Costs that do not vary with the number of patients will be categorized as fixed costs, whereas those that vary by the number of patients will be defined as variable costs. The costs of the CGM implementation will be compared to costs under a control scenario. We will estimate the potential costs and cost savings resulting from the CGM implementation.

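### RQ 2 as designed cannot test a significant reduction in nursing workload; separately, RQ 1 adoption is defined in two different ways

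*Combined protocol and SAP*

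**What the plan says.** **RQ 2.** The Objectives state the hypothesis "The use of CGM will significantly reduce nursing workload while increasing frequency of glucose monitoring" and name the means: "We examine nursing workload and care delivery factors through surveys administered to MICU nurses", together with a focus group of 10 nurses. The RQ 2 procedures in III.C list three implementation scales (AIM, IAM, FIM), a satisfaction questionnaire adapted for healthcare workers, and the focus group. They then state: "All Aim 2 variables and measures appear in Table 2". On the focus group they say: "A semi-structured interview guide will focus on areas of perceived CGM implementation support and education, CGM knowledge, and recommendations for future best practice". All 152 MICU nurses are invited to the survey. The nurse schedule of activities has one variable row, "Evaluation of CGM support", with frequency given as once.

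III.D Data Analysis opens with a general statement, "Descriptive statistics will summarize the sample characteristics and distribution of each variable". For RQ 2 itself it describes only the focus group analysis, where "a code book will be developed a priori based on the semi-structured interview questions".

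Under exploratory RQ 4, III.C names nursing time under CGM versus POC monitoring as a resource outcome. It also mentions nursing productivity and burden, and refers to a time-and-motion study as a data source.

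**RQ 1.** The Objectives define adoption as patients who consent divided by patients eligible. The RQ 1 variables in III.C and the patient schedule of activities define it as patients approached divided by patients eligible. A further row of that schedule, under fidelity and adoption, uses total initiations as its denominator.

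**The concern.** A claim that something is significantly reduced needs a measure of it, a level to reduce it from, and a test. RQ 2 appears to specify none of the three for workload. Nurse work patterns are in the study title, so readers will look for this conclusion. A survey of nurses already using CGM, with nothing to compare against, could be reported as support for it.

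The adoption question is separate. If the procedures and schedule are followed, the adoption figure will count patients whom the study team reached, whether or not they accepted CGM. In a hybrid type II study, adoption is a headline implementation outcome, so the choice of numerator matters.

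**Working it through.** **1. The plan's own power figures.** The only power statement (III.B, Sample Size Justification) concerns percent time in 70–180 mg/dl. Power is Φ(δ / (SD·√(2/100)) − 1.960), with 100 per group and two-sided alpha 0.05.
- SD 25, δ 10: 10/3.536 = 2.828, power 80.7% (stated 80%).
- SD 15, δ 10: 10/2.121 = 4.714, power 99.7% (stated 99%).
- SD 15, δ 7: 7/2.121 = 3.300, power 91.0% (stated 90%).

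The figures reproduce. They belong to RQ 3 and give no support to a workload test.

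**2. What a workload test needs, and where it stands.**

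| Element | RQ 2 | RQ 4 (exploratory) |
|---|---|---|
| Measure | Acceptability, appropriateness, feasibility, satisfaction, support, knowledge; no workload row in either schedule as extracted | Nursing time; productivity and burden with no instrument |
| Comparator | None: nurses in the CGM-enabled MICU, no baseline | CGM versus POC named; source of the POC observations not described |
| Test | Qualitative coding; general descriptives | None stated for nursing time |
| Link to the RQ 2 hypothesis | – | None |

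The stated topics of the interview guide do not include workload either.

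**3. Can earlier evidence stand in?** The Background reports less POC testing in earlier inpatient CGM studies. The CGM + POC Protocol section sets validation every 4 hours here, against every 6 hours in the earlier local protocol.
- This protocol: 24/4 = 6 scheduled tests on a full validated day.
- Earlier local protocol: 24/6 = 4.
- Ratio: 6/4 = 1.5, or 50% more.

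Table 1 adds tests during initial validation, after listed clinical events and after some alerts. Both schedules are CGM schedules, so the 50% says nothing about POC-only care. The documents give no POC-only testing rate. Scheduled tests would be fewer than in controls only if controls averaged more than 6 per day, so the direction is open.

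**4. What a descriptive survey could deliver.** The 95% half-width for a proportion near 50% is 1.96·√(0.25/n). The response rates are assumed.
- All 152 respond: ±7.9 points.
- 76 respond (50%): ±11.2 points.
- 46 respond (30%): ±14.4 points.

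That is usable precision for perceived workload, provided that it is asked about.

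**5. Adoption.** Let E be eligible, A approached and C consented. Then C/E = (A/E)·(C/A), so the approached ratio exceeds the consented ratio by 1/(C/A). The documents give no consent rate, so a range is assumed.
- Consent 90%: 1/0.9 = 1.11.
- Consent 70%: 1/0.7 = 1.43.
- Consent 50%: 1/0.5 = 2.0.

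For example, with an assumed 80% approached and 60% of those consenting, the procedures would report 80% and the Objectives 0.8 × 0.6 = 48%. The two agree only if everyone approached consents.

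**6. The fidelity and adoption row.** Its denominator, total initiations, matches neither adoption ratio. Nor does it match the fidelity ratio in the Objectives and RQ 1 variables, which divides non-adjunctive uses by occasions when such use was indicated. That fidelity ratio has no row of its own in the schedule as extracted.

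**The case against.** The best reply is that workload is not ignored. RQ 4 names a nursing-time outcome with a CGM versus POC contrast. This stands, and it rules out a stronger reading that a reader might infer from RQ 2 alone: that the documents contain no workload outcome anywhere. The defect is narrower. That outcome is exploratory, its source study has no stated sample, schedule, comparator or test, and nothing ties it to the RQ 2 hypothesis.

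A second reply is that the operative text is softer. The RQ 2 procedures speak of assessing the degree of effect and, unlike those for the other three questions, do not repeat the hypothesis. The primary objective is feasibility, and the power statement concerns time in range. This limits the damage, but the Objectives still predict a significant reduction.

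A third reply is that the survey items are not shown, several will be modified, and the tables are visibly broken in the extracted text. Workload items may therefore exist or be added, and the single stated frequency is printed against one row only. It would go too far to conclude that workload is certainly never asked about. Even so, items put to nurses in the CGM unit, with no baseline or POC-only comparison, could describe perceived workload but not test a reduction.

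On adoption, approach depends on permission being granted, so the approached ratio is not purely a count of staff effort. It still does not count acceptance of CGM.

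**Conclusion.** The point holds on both counts. The workload hypothesis cannot be tested by RQ 2 as written, and adoption has two incompatible numerators.

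No size can be put on the workload gap, because the documents give no workload effect, variability or POC-only rate. A reader might infer from the tighter testing schedule that CGM will add to nurses' work here. The documents do not support that, because the 6 versus 4 tests compare two CGM protocols.

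For adoption, the approached ratio is 1.11 to 2.0 times the consented ratio over assumed consent of 90% to 50%.

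The conclusion on RQ 2 rests on the instruments being as described and on the schedules being complete as extracted. The time-in-range power calculation is unaffected.

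**What to change.** **RQ 2.** Choose one of two routes.
- Restate the workload hypothesis as descriptive (nurses' perceived workload), include workload items or interview questions, and drop the claim of a significant reduction.
- Link RQ 2 to the RQ 4 nursing-time outcome, and specify the time-and-motion study's tasks, sample, POC comparator and test.

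Optionally, report POC tests per patient-day from the EHR descriptively, as a partial proxy. State that the CGM patients' count is largely set by the protocol schedule.

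**RQ 1.**
- Use consented/eligible for adoption in the Objectives, the RQ 1 variables and the patient schedule.
- Report approached/eligible separately as reach.
- Reconcile the fidelity and adoption row with the stated fidelity ratio, and give that ratio its own row.

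**Cost.** The descriptive route and the adoption fix are mainly wording changes plus a few survey or interview items. The time-study route also needs observer hours. The downside is a more modest RQ 2 conclusion and, unless everyone approached consents, a lower reported adoption figure. Nothing here changes testing frequency or patient care.

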Sample Size Justification. The primary outcome for the power analysis is the percentage of time spent in target (70-180mg/dl). We estimate from previous studies^{13,28} that these values may have a standard deviation as high as 25 percentage points, in which case with 100 patients in each group we will have 80% power to detect a difference of 10 percentage points in time in range (e.g., 65 vs. 75); a moderate effect size of 0.4. If the standard deviation is lower (e.g., 15 as has been true in some studies), we will have greater power (99%) to detect a 10 point difference and are still well powered to detect smaller differences (e.g., 90% power for a 7 point difference). All power calculations assume an alpha of 0.05 and minimal statistical effects of clustering within the hospitals (e.g., unit or nurse level).

C. Detailed study procedures

Recruitment: Critical care clinical research coordinators will screen for preliminary eligibility and forward potential participant names to study team using a secure medical record in-basket process. The study team will determine eligibility. The study team will ask for permission for the patient to be approached. If permission is granted, the study team will verify eligibility and obtain informed consent from the patient or the patient's legally authorized representative. Consent will be obtained prior to research participation and CGM placement. Recruitment is expected at a rate of 5 patients per week over seven months. Our target recruitment will be 100 MICU patients.

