Procedures. Glucose data will be directly transferred from the MICU patients (N=100) to Android mobile phones/Dexcom G6 app which captures and stores glucose values every 5 minutes (up to 288 values/day for 100% CGM wear). CGM data is automatically transferred from phones/Dexcom G6 app to Dexcom Clarity. Individual patient discrete data will be downloads directly from the Clarity site. Historical controls meeting the gateway criteria (glucose >250 mg/dl or on IV insulin during admission) from the same MICU will be matched on the following factors: Diagnosis and type of diabetes, home insulin use, steroid use during hospitalization, vasopressor use, North vs. South MICU wings (NP team floor vs. resident team floor, respectively), and diabetic ketoacidosis (DKA)/hyperosmolar hyperglycemic syndrome (HHS) status. POC glucose values for historical controls (N=100) will be obtained directly from OSUWMC EHR. EHR data will be obtained through an information warehouse request providing time stamped, POC glucose value for each match patient. All data will be uploaded into STATA 15.0 where it will be cleaned and merged prior to analysis.

Variables and Measures. Demographic, admission, and diabetes specific variables of interest appear in Table 2 and will be collected from the EHR for MICU participants and for historical controls. Clinical condition variables will include presence of renal replacement, mechanical ventilation, ECMO, associated cardiac arrest or cerebrovascular accident and SOFA score. SOFA score was calculated, though noted to have limited discriminant function for predicting mortality.³² The SOFA score has been validated in critically ill patients³³, and is currently the scoring system recommended by the Sepsis 3 definition.³⁴ CGM and POC glucose data will be aggregated into glucose ranges and thresholds as described in Table 2.

Exploratory aim:

RQ 4: To assess hospitalization outcomes and conduct economic evaluation of the costs to deliver CGM implementation in the MICU.

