Rational/Approach. We will explore the impact of CGM therapy using a CGM + POC protocol on patient hospital outcomes and costs. Analyzes the economic aspects inpatient CGM on patient health and healthcare interactions, with a focus on the costs (inputs) and consequences (outcomes) of CGM will enable full understanding of implementation effects. We hypothesize that patients with CGM will experience shorter length of stay, lower cost of stay, will be more likely to discharge to home vs. SNF, have a lower 30-day readmission rate, and experience lower mortality/morbidity than matched patients receiving fingerstick POC.

Procedures. Data will be retrospectively extracted from the EHR for patients using CGM in the MICU (N=100) along with 100 historical controls. Data will be obtained from the EHR and billing department through an information warehouse request. Data from the time in motion study will be evaluated to extrapolate the economic impact of nursing personnel time spent for CGM vs. POC glucose monitoring and resources used in POC vs. CGM glucose monitoring.

Variables and Measures. *Hospital outcomes criteria* include the following: Length of stay [ICU, total stay], cost of stay, discharge level of care [home, SNF], morbidity, mortality and readmission rate at 30 days. We will conduct economic evaluation of the costs to deliver CGM implementation in the MICU. We will track resources needed for CGM implementation including personnel, training, facilities, materials, equipment, and other necessary inputs. In addition to resources used, we will expand analysis to evaluate nursing productivity and burden. *Resource outcomes criteria* include: nursing time spent in CGM vs. POC glucose monitoring and cost of CGM vs. standard POC glucose monitoring materials.

Table 2. Patient Participant Schedule of Activities

Aim	Concept	Variable	Frequency	Measure	
Aim 1	Clinical utility criteria	Time to CGM validation (Aim 1 only)	Sensor placement (Q10 days)	
 • EHR • Clarity download 	
		Mean percent of dosing decisions determined by CGM	Daily		
		Changes in insulin dosing from guideline or outside standard times in response to alarm and/or trend data	Daily		
Aim 1	Fidelity & Adoption Implementation criteria	Proportion of times CGM initiated or patient approached for study inclusion according to protocol/total number of initiations	Admission	
 • EHR • Study recruitment log 	

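### Controls are matched on six factors, but apart from possibly MICU wing the matching enters neither the RQ3 model nor any RQ4 outcome comparison; if the factors predict glucose, the analysis is conservative and forgoes precision.

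*Combined protocol and SAP*

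**What the plan says.** The RQ 3 Procedures (III.C) match historical controls from the same MICU on diabetes diagnosis and type, insulin use at home, steroids, vasopressors, North or South wing, and DKA/HHS status. The number of controls is given there too: "POC glucose values for historical controls (N=100) will be obtained directly from OSUWMC EHR". No matching ratio or algorithm is stated.

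For the analysis, Objectives RQ 3 says CGM patients will be "compared to matched historical control patients using 3-tiered linear mixed models to control for patient, unit, and nurse specific variability". Data Analysis (III.D) names the same three tiers for the daily CGM measures and says the modelling will be repeated for the controls' POC measures. It writes no matched-set term and does not list the matching factors as covariates. Patient-condition covariates (SOFA score, renal replacement, ventilator support, pH) are named only for RQ1.

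RQ 4 (III.C) expects that CGM patients will "experience lower mortality/morbidity than matched patients receiving fingerstick POC", along with better length of stay, cost, discharge and readmission outcomes. Data Analysis then describes a cost analysis only. It gives no comparative model, matched or adjusted, for the hospital outcomes.

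The Sample Size Justification (III.B) says that "with 100 patients in each group we will have 80% power to detect a difference of 10 percentage points in time in range". It considers clustering by unit or nurse and does not mention matching.

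**The concern.** Matching on predictors of the outcome makes matched patients resemble one another. The difference between group means then varies less than it would between two independent samples. An analysis that contains neither the matched sets nor the matching factors does not see this: it leaves the variation they explain in the residual and reports a standard error suited to an unmatched design.

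At stake are intervals and p-values that do not reflect the design, and precision that the study has worked to obtain but does not use. For RQ4 binary outcomes the effect is slightly different. If they are compared by odds ratio, leaving out prognostic matching factors also pulls the estimate toward the null.

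**Working it through.** **Inputs from the documents.** 100 patients per group, a 10-point difference and 80% power (III.B). On the SD, "these values may have a standard deviation as high as 25 percentage points"; the alternative is SD 15, with 99% power for 10 points and 90% for 7 points. On the error rate, "All power calculations assume an alpha of 0.05 and minimal statistical effects of clustering within the hospitals". Data Analysis adds: "Two-sided significance level of 0.05 was used for all the statistical tests".

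**Input not in the documents.** The within-pair correlation ρ of the outcome. I take 0 to 0.3 as an assumption. With exact matching, ρ equals the share of outcome variance that the matching factors explain, so 0.3 means the six factors explain 30%.

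**Step 1: reproduce the stated power.** For two independent groups, SE = SD × √(2/100) and power = Φ(difference/SE − 1.96).
- 10 points, SD 25: SE = 3.536, power 80.7% (80.4% with the noncentral t). Stated 80%.
- 10 points, SD 15: 99.7%. Stated 99%.
- 7 points, SD 15: 91.0%. Stated 90%.

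A one-sided test would give 88.2% in the first case, which does not fit. The stated figures are therefore two-sided, independent-groups calculations with no allowance for matching.

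**Step 2: the same data with matching** (difference 10, SD 25, 100 matched pairs, normal approximation).
- True SE = 3.536 × √(1 − ρ).
- Overstatement of the SE when matching is ignored = 1/√(1 − ρ) − 1.
- Actual type I error when ignored = 2 × [1 − Φ(1.96/√(1 − ρ))].
- Actual power when ignored = Φ((10 − 1.96 × 3.536)/true SE).
- Power when used = Φ(10/true SE − 1.96).

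| ρ | True SE | SE overstated | 95% half-width, ignored / used | Type I error, ignored | Power, ignored | Power, used |
|---|---|---|---|---|---|---|
| 0 | 3.536 | 0% | 6.93 / 6.93 | 5.0% | 80.7% | 80.7% |
| 0.1 | 3.354 | 5.4% | 6.93 / 6.57 | 3.9% | 82.0% | 84.7% |
| 0.2 | 3.162 | 11.8% | 6.93 / 6.20 | 2.8% | 83.4% | 88.5% |
| 0.3 | 2.958 | 19.5% | 6.93 / 5.80 | 1.9% | 85.0% | 92.2% |

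Worked row, ρ = 0.2: true SE = 3.536 × √0.8 = 3.162. Ignored: (10 − 6.93)/3.162 = 0.971, so 83.4%. Used: 10/3.162 − 1.96 = 1.202, so 88.5%.

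**Step 3: what is forgone.** The last two columns differ by about 3, 5 and 7 percentage points of power at ρ = 0.1, 0.2 and 0.3. Every entry is at or above 80.7%.

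**The case against.** The best case against the point has five parts.

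- **Pairing is not stated.** A reader might infer one-to-one matching from 100 and 100. The documents suggest it but give no ratio, algorithm or pair, and frequency matching is not excluded. This stands, and the fix must work under either. It does not remove the point, because under frequency matching the factors still belong in the model.
- **No estimator of the difference is written.** Data Analysis fits the model to CGM data and repeats it for controls, with no joint model or group term. A reader might conclude that the reported interval will be too wide; strictly, there is no specified interval yet. That gap comes first. But Objectives RQ 3 promises a comparison with matched controls using these models, so the matching must be settled when the comparison is written.
- **The error is on the safe side.** A reader might infer that planned power is lost or that false positives rise. Neither follows: with non-negative correlation, type I error stays at or below 5% and power at or above the planned 80%. What is forgone is a gain the plan never claimed.
- **The size is assumed.** The documents give no correlation. Exclusion of patients under active treatment for DKA or hyperosmolar state probably leaves the DKA/HHS factor little variation among CGM patients, and percentages from a few POC values per day are noisy. Both argue for the lower end of the range. This stands.
- **Other forces act on precision.** Clustering works the other way: assumed design effects of 1.1, 1.2 and 1.5 would give 76.9%, 73.3% and 63.7% power. So the net error of the plan's precision is not established. That is a reason not to raise the power claim; it does not justify omitting the factors.

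It is also fair that wing is one of the six factors and that the unit tier may be the wing, though the plan does not define it.

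**Conclusion.** The point holds in a limited form. Six matching factors are specified, and at most one of them reaches the RQ3 model. RQ4, which is exploratory, has no matched or adjusted comparison of hospital outcomes, and the power is an independent-groups figure. If matched patients' outcomes are positively correlated, an analysis that ignores this is conservative by the amounts tabulated above; if the correlation is zero, it costs nothing.

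These sizes rest on an assumed correlation, exact matching, equal SDs in the two groups and no clustering. They concern a difference in means and do not carry over directly to RQ4 odds ratios. This is a matter of efficiency and of aligning analysis with design. It is worth correcting because it is nearly free; it does not threaten the stated power.

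**What to change.** 1. State the matching ratio and algorithm, and say what the unit tier is.
2. In the single RQ3 model that contains the CGM-versus-control term, include the six matching factors as fixed covariates. This is valid under individual or frequency matching.
3. If matching is individual, add a matched-set random effect and store the set identifier when controls are selected. The random effect already accommodates a set that loses a member, so no switch of method is needed.
4. Adjust the RQ4 outcome comparisons for the same factors. If pairs exist, matched-set methods are an alternative: conditional logistic regression or McNemar's test for binary outcomes, paired or mixed models for cost.
5. Keep 80% as the conservative power figure with respect to matching. If a gain is shown, show it over a range of correlations labelled as assumed.

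The cost is SAP wording, at most one extra column in the analysis file, and a few model degrees of freedom. The factors must be recorded for the matching anyway, and neither sample size nor patient care changes.
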